Appendix IV. Investigator's Brochure

- none available for [¹¹C]raclopride
- See attached file of Morphine Package insert

Appendix VII. Results from mouse study

Individual probe placements in the nucleus accumbens (NAc) and dialysate DA levels in response to systemic morphine (3' 10 and 30 mg/kg, i.p.) in h/mOPRM1-118AA and h/mOPRM1-118GG mice.

Repeated measures ANOVA (with genotype as a between-factor and drug doses and time as within-factors) conducted for DA time course data showed significant main effect of dose ($F_{(3,6)} = 34.6$; $p < 0.001$) and genotype ($F_{(1,6)} = 8.98$; $p = 0.024$), indicating that NAc DA increased dose-dependently following morphine injections and overall response was different between two genotypes. Repeated measures ANOVA (genotype – between-factor, dose – within-factor) conducted for area under the curve (AUC) DA data revealed significant main effect of genotype ($F_{(1,14)} = 4.38$; $p = 0.05$) and dose x genotype interaction ($F_{(2,14)} = 4.06$; $p = 0.037$), as well as significant simple effect of genotype for DA response to the second drug dose ($F_{(1,14)} = 7.31$; $p = 0.02$). Overall, these results indicate that NAc DA response to systemic morphine was significantly reduced in h/mOPRM1-118GG genotype as compared with h/mOPRM1-118AA genotype.

Repeated measures ANOVA (genotype – between-factor, dose and time – within-factors) conducted for LMA time course data revealed significant main effect of dose ($F_{(3,18)} = 62.5$; $p < 0.001$) and dose x genotype interaction ($F_{(3,18)} = 3.62$; $p = 0.05$). Repeated measures ANOVA (genotype – between-factor, dose – within-factor) conducted for LMA AUC data also showed significant main effect of dose ($F_{(2,18)} = 68.9$; $p < 0.001$) and dose x genotype interaction ($F_{(2,18)} = 4.5$; $p = 0.035$); however, simple effects of genotype for each dose separately were not significant. Overall, these results indicate that systemic morphine administration dose-dependently increased LMA and these increases were reduced in h/mOPRM1-118GG genotype as compared with h/mOPRM1-118AA genotype.

Appendix X. Plan for clinical monitoring of participants receiving morphine at NIDA:

Note: Equivalent medications and equipment may be substituted with those listed here based on need and availability. This document is a guideline and all numbers provided herein are guidelines and must be accompanied by sound clinical judgment when decisions are made.

Equipment/medications to be available:

1. Crash cart with multiple doses of naloxone
2. 1mg/ml Naloxone hydrochloride injection USP, for intravenous, intramuscular and subcutaneous administration
 - a. Ten 2 mL single dose disposable prefilled syringes, in the MIN-I-JET® system with 21 G. x 1 1/2" needle. Boxes of 25. NDC 76329-1469-5, Stock No. 1469 (contains no preservative), or
 - b. Ten 2 mL single dose disposable Luer-JetTM Luer-Lock Prefilled Syringe. Shrink Wrapped Packages of 10. NDC 76329-3369-1, Stock No. 3369 (contains no preservative)
3. Epinephrine IM (EpiPen, Adrenaclick, Twinject, etc.)
4. Diphenhydramine 25-50mg PO or 10-50mg IV/IM
5. Ranitidine 150mg PO or 50mg IV/IM
6. Ondansetron ODT (Orally Disintegrating Tablets) 4mg
7. Solumederol 8mg PO or prednisone 10mg PO
8. Supplemental oxygen tank with tubing
9. Nasal cannula
10. Venturi mask
11. Pulse oximeter
12. Portable blood pressure/heart rate monitor
13. Normal saline (3 bags)
14. Electrocardiogram machine

Plan:

1. Personnel with NIH medical credentials (MD, PA, or RN) and ACLS certification as well as the investigator administering the tests will be in the room with the participant from 5 minutes before the injection until 30 minutes after the injection.
2. Participant's respiratory rate and oxygen saturation will be continuously monitored by pulse oximetry.
3. If participant's oxygen saturation level drops below 94% for >1-2 minutes, he will be given supplemental oxygen. If the oxygen saturation level improves, the participant will be allowed to continue the study.

4. If participant's oxygen saturation level drops and remains below 90% for >1-2 minutes or his respiration rate drops below 8 breaths/min, or s/he becomes sedated and difficult to arouse the following will be done:
 - a. Discontinue morphine.
 - b. Administer supplemental oxygen by Venturi mask
 - c. If no improvement, administer Naloxone 0.2-0.4mg IV/IM/SC .
Additional Naloxone 0.2-0.4mg IV/IM/SC may be administered every 2-3 minutes if no response. Given the short half-life of naloxone (30-90 mins), naloxone will be repeated if vital signs or participant condition indicates re-sedation prior to arrival of emergency personnel.
 1. If participant does not respond to above measures, call 911 and transport to the Johns Hopkins bayview Emergency Room
 2. Participant will be disqualified from the study.
5. If participant vomits or feels excessively nauseous, he will be disqualified from the study.

Appendix XI. Plan for clinical monitoring of participants receiving morphine at the NIH Clinical Center in the Course of PET sessions

Note: Equivalent medications and equipment may be substituted with those listed here based on need and availability. This document is a guideline and all numbers provided herein are guidelines and must be accompanied by sound clinical judgment when decisions are made.

1. Rapid Response Team (ICU staff) receive a courtesy call notifying them in advance of the time and location for this study session by the Research Coordinator.
2. The ACLS certified physician responsible for the participant and drug administration has called the RRT and given a brief clinical report and confirmed dosing time.
3. A full stocked Code Cart remains in the designated area in Interventional Radiology (including a suction device), 40 Seconds walking distance from the PetScan room.
4. A full stocked, ACLS Code Cart Tray provided by Pharmacy will remain in the PetScan room for the duration of the session, by the Clinical Nurse manager
5. Emergency drugs, prepared for immediate administration have been provided to our ACLS physician to be held by this M.D. on hand for the duration of the study session, including Naloxone, Atropine and Ondansetron.
6. A bell will be given to the participant once in the PET Scanner with proper instructions to use at any point in time during the study session as a means to signal distress in addition to free verbal expressions.
7. Code cart with multiple doses of naloxone
 - a. 1mg/ml Naloxone hydrochloride injection USP, for intravenous, intramuscular and subcutaneous administration. Initial naloxone dose should be 0.4mg, and subsequent doses 0.4-2.0mg. The rationale for starting with the lower dose is to avoid precipitating an opioid withdrawal reaction should the subject have a high degree of tolerance due to the use of some synthetic opioid that has remained undetected by our biochemical tests.
 - b. Ten 2 mL single dose disposable prefilled syringes, in the MIN-I-JET® system with 21 G. x 1 1/2" needle. Boxes of 25. NDC 76329-1469-5, Stock No. 1469 (contains no preservative), or
 - c. Ten 2 mL single dose disposable Luer-JetTM Luer-Lock Prefilled Syringe. Shrink Wrapped Packages of 10. NDC 76329-3369-1, Stock No. 3369 (contains no preservative)
8. Atropine sulphate IV: 1mg/ml
Dose of 0.5 ml IV push PRN for acute symptomatic bradycardia. This dose may be repeated every 3 to 5 minutes up to a maximum total dose of 3 mg
9. Epinephrine IM: (EpiPen, Adrenaclick, Twinject, etc.)
10. Diphenhydramine: 25-50mg PO or 10-50mg IV/IM
11. Ranitidine: 150mg PO or 50mg IV/IM
12. Ondansetron: 2mg/ml. Dose 4 mg IV push PRN nausea and/or vomiting
13. Solumederol 8mg PO or prednisone 10mg PO
14. Supplemental oxygen with tubing, in the PetScan room attached to the wall.

15. Nasal cannula
16. Venturi mask
17. Pulse oximeter
18. Portable blood pressure/heart rate monitor
19. Normal saline (3 bags)
20. Electrocardiogram machine

Plan:

1. Personnel with NIH medical credentials (MD, NP, or RN) and ACLS certification as well as the investigator administering the tests will be in the room with the participant from 5 minutes before the injection until 60 minutes after the injection.
2. Participant's respiratory rate, oxygen saturation, heart rate and blood pressure will be continuously monitored.
3. If participant's oxygen saturation level drops below 94% for >1-2 minutes, he will be given supplemental oxygen which will be adjusted to reach a target saturation of 94% or higher. If the oxygen saturation level improves, the participant will be allowed to continue the study.
4. If participant's oxygen saturation level drops and remains below 90% for >1-2 minutes or his respiration rate drops below 8 breaths/min, or s/he becomes sedated and difficult to arouse the following will be done:
 - a. Discontinue drug administration if still ongoing, terminate study session, and rapidly remove subject from the scanner bed to a position that allows adequate observation and access for procedures.
 - b. Administer supplemental oxygen by Venturi mask, adjusting it to achieve a target saturation of 94% or higher. If no improvement, administer Naloxone 0.4mg IV/IM/SC and call the Code team.
 - c. Observe for signs of precipitated withdrawal due to use opioid use that has been undetected by drug screens. If no signs of withdrawal, additional Naloxone 0.4-2.0 mg IV/IM/SC may be administered every 2-3 minutes if no response. Given the short half-life of naloxone (30-90 mins), naloxone will be repeated if vital signs or participant condition indicates re-sedation prior to arrival of emergency personnel.
5. If participant displays clinically significant bradycardia, hypotension or a clinically significant combination thereof, Initiation of the standard ACLS algorithm and the Code team will be called for treatment of these conditions, i.e. atropine 0.5mg IV push, may repeat up to a total dose of 3mg. If there is not an adequate response to this intervention, consider initiating the next step of the standard ACLS algorithm, i.e. administration of epinephrine, and initiating IV fluid.
6. If participant displays any of the problems above, vomits or feels excessively nauseous, or displays any other adverse reactions such as e.g. excessive sedation, anxiety or allergic symptoms and these cannot be adequately managed, (the subject will be removed from the scanner [note: Clinical Center version]) any ongoing research procedures will be discontinued, and subject will be placed in a position that ensures free airways, adequate observation, and access for procedures.

Revised 3/20/2014

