During Visit 2, physiological responses (RR, HR, EKG and oxygen saturation) will be monitored using standard instrumentation (EKG, pulse oximetry) continuously for 60 min after injections or until they return to normal and values for these parameters as well as for BP will be recorded approximately every 5 min for the duration of the drug effect. In addition, physiological responses will be collected continuously on the AutoSense, a wearable suite of sensors for physiological monitoring in the daily environment. AutoSense was developed by a group of computer scientists at the University of Memphis, led by [name]. Parameters measured by AutoSense include respiration rate, heart rate, heart-rate variability, skin conductance, and activity level. The sensors are hosted on a tiny computing platform called a wireless sensor mote (with dimensions similar to those of the memory cards used in digital cameras). Sensors are attached to an elastic belt that is worn around the chest. Two electrodes, similar to those used in ECGs, are placed on the chest and connected to the sensors in the belt. Data are

sent wirelessly to a pre-programmed smart phone for temporary storage. These data collected during administration of morphine under controlled laboratory conditions will be used to develop an algorithm to detect opioid administration in future field studies.

MRI scans:

All MRI scans will be performed in the Trio at the BRC. The participants will not receive any drug before these scans. Under this protocol or 10-DA-N457, a structural MRI of the brain for co-registration with the PET scan as well as resting state and DTI MRI scans of the brain will typically be obtained on the day of Visit 1 or 1a at the BRC. As many participants enroll in multiple studies, the participant may have already enrolled in 10-DA-N457 and the scans acquired under that protocol may have already been performed and will be used for this protocol.

Repeating the MRI scans - Because excessive head movement is an obstacle to obtaining quality fMRI data, participants who generate unusable data (or if there is an equipment failure) during their scanning session may be asked to repeat the session. Repeating the session will maximize the risk/benefit ratio of the MRI scanning as it will allow completion of all aspects of the study.

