The participant will be returned to the lounge for a relaxation period and a snack or lunch. In early afternoon, the participant will return to the study room for the morphine injection, which will be administered by an NIH Credentialed physician with ACLS certification. Participants will receive an injection of 10 mg/70 kg morphine (2 mg/ml) administered by an NIH Credentialed physician over 1 minute. The tests described above will be repeated. The participant will be monitored by an NIH Credentialed physician for the next 60 min or until HR, RR, BP, EKG and oxygen saturation have returned to normal ranges. Values will be recorded approximately every 5 min (+/- 1) for the next 60 min after the injection or until they have returned to normal ranges.

Table for Visit 2

Minutes	BL	0	5	10	15	20	25	30	35	40	45	50	55	60 (plus additional records q. 10 min if not within normal range)
Morphine or placebo administration		x												
HR, BP, RR, O2 Sat, EKG recorded *	x		x	x	x	x	x	x	x	x	x	x	x	x
Cold Pressor Test			x											
DEQ	x			x		x		x		x		x		x
Pupil constriction	x			x		x		x						
Blood draw for ACTH/cortisol* *	x		x				x							
VAS														x

Please note the timing for these parameters will be as close as possible to the stated times, but may not be at exactly these times. Data from cold pressor test, DEQ and pupillary constriction will be collected in sequence, not at the same time.

*Please note monitoring of these parameters will be continuous until they have returned to normal ranges and recording of these parameters will continue at 10 min intervals if they have not returned to normal ranges. It is expected that following the placebo injection, these values will be normal throughout the study, but they will be monitored for at least 60 min.

** First blood draw for ACTH/cortisol will be after cold pressor test and DEQ, but before pupil constriction test.

The AutoSense electrodes and respiration belt will be removed at the end of the session.

Visits 3 and 4: PET studies of [¹¹C]raclopride binding with and without morphine:

Participant will be brought to the Clinical Center via taxi during the afternoon or early evening of each day before the scheduled PET studies.

Outline of PET session procedures:

- 1) Two IV lines will be started, one for injection of [¹¹C]raclopride, the other for the morphine or placebo (normal saline in a volume equal to that used for the morphine injection) injection.

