The potential adverse consequences of the morphine injection primarily involve respiratory depression, skeletal muscle rigidity, hypotension, bradycardia, nausea, dizziness or other impairment. Following the morphine injection, oxygen saturation, respiratory rate, blood pressure, and heart rate will be monitored continuously by an NIH Credentialled physician with ACLS certification for 60 min or until these values have returned to normal ranges. Values will be recorded approximately every 5 min until they have returned to normal ranges. Subjects who experience significant nausea, breathing difficulties, hypotension, or bradycardia will carefully monitored and supplemental oxygen, intravenous fluids, atropine, and naloxone will be available if needed. Finally, risks of impairment are minimized by monitoring subjects until the effects of the opiate on motor performance or judgment have passed, and sending subjects home in a taxi.

The study is designed to provide the first opiate challenge in the outpatient clinic, so that persons who react unfavorably to the challenge will be identified and excluded before becoming eligible for the PET scan procedure. Participants will be expected to be intoxicated at the conclusion of the opiate challenge. They will be supervised on site until any signs of drug effect have dissipated (e.g., vital signs in normal range and no signs of impairment) and the participant reports that they are not experiencing any drug effects at which time they should be able to safely to leave the NIH premises and will be taken home in a taxi arranged and paid for by the NIH.

PET scan:

Potential risk of this procedure is primarily related to radiation exposure. The effective dose from the emission and transmission scans will be 0.62 rem, which is below RSC guidelines of 5.0 rem per year in adults. This risk has been assessed by separate Radiation Safety review, which assures that exposure is minimized, and falls within a widely accepted range. In summary, no harmful effect to humans has been observed from the levels of radiation used here. Additional measures taken to ensure subject safety will be to obtain a careful history of exposure to radiation from other sources or medical procedures to ensure that total exposure remains within an acceptable range.

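### Appendix X asks for in-room attendance only to 30 minutes after the Visit 2 morphine injection, against 60 minutes in Appendix XI for the same dose; changing 30 to 60 is a minor, cheap safety-consistency correction

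*Combined protocol and SAP*

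**What the plan says.** Visit 2 takes place at the Baltimore site (Section 4d), so Appendix X governs its morphine injection. Plan item 1 there states that credentialed, ACLS-certified personnel (MD, PA or RN) and the investigator administering the tests "will be in the room with the participant from 5 minutes before the injection until 30 minutes after the injection". The note at the head of Appendix X describes the document and all its numbers as guidelines, to be applied with clinical judgment.

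Appendix XI covers the PET sessions at the Clinical Center and carries the same note. Its Plan item 1 says that the equivalent staff "will be in the room with the participant from 5 minutes before the injection until 60 minutes after the injection".

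The body text uses 60 minutes for Visit 2. In Section 4d each man is "monitored by an NIH Credentialed physician for the next 60 min or until HR, RR, BP, EKG and oxygen saturation have returned" (that is, are back within normal limits), and the vital parameters are to be "monitored using standard instrumentation (EKG, pulse oximetry) continuously for 60 min after injections or until they return to normal". The footnote to the Visit 2 table adds that "recording of these parameters will continue at 10 min intervals if they have not returned to normal ranges". Section 7, under the steps to minimize risk, says that after morphine the vital parameters "will be monitored continuously by an NIH Credentialled physician with ACLS certification for 60 min or until these values have returned to normal ranges".

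**The concern.** Two near-identical sentences give different attendance times after the same dose, and the shorter one belongs to the visit where morphine is given for the first time in the study. Section 7 explains that purpose: "The study is designed to provide the first opiate challenge in the outpatient clinic", so that men who react badly are found before they reach the scanner. The same section names respiratory depression as the most important medical risk.

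Backup also differs between the sites. In Appendix X the last step, if oxygen and naloxone fail, is a 911 call and transport to a nearby emergency room. In Appendix XI the Rapid Response Team is told of the session in advance and a Code team can be called. The site with less backup described therefore has the shorter in-room figure.

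What is at stake is what the site's own operating plan tells staff to do. Someone working from Appendix X alone would find a shorter period of required presence than the body text's monitoring commitment suggests.

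**Working it through.** No statistical figure is involved, so the check sets the statements side by side.

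| Place | Who and what | Time after morphine |
|---|---|---|
| Appendix X, Plan item 1 (Visit 2) | ACLS-certified MD, PA or RN, and test investigator, in the room | 30 min |
| Appendix XI, Plan item 1 (PET sessions) | ACLS-certified MD, NP or RN, and test investigator, in the room | 60 min |
| Section 4d, Visit 2 | Credentialed physician, monitoring | 60 min or until normal |
| Section 4d, PET procedure | ACLS-certified physician, monitoring | 60 min or until normal |
| Section 7, steps to minimize risk | ACLS-certified physician, continuous monitoring | 60 min or until normal |

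1. **Same exposure.** Section 4 gives 10 mg/70 kg over 1 minute at Visit 2 and describes the PET injection as the same procedure. Section 7 limits each day to one dose of that size. Dose does not explain the difference.
2. **Size of the difference.** 60 − 30 = 30 minutes of stated in-room presence.
3. **Which figure is the outlier.** Appendix XI's 60 minutes matches the monitoring period in its own body text. Appendix X's 30 minutes matches no monitoring period in the body text.
4. **Is a reason given?** None appears in Appendix X, Section 4d, Section 7 or Section 8.
5. **Does supervision end at 30 minutes?** No. Besides the physician commitment, Section 4d has a nurse monitoring throughout Visit 2. Section 7 says of the participants: "They will be supervised on site until any signs of drug effect have dissipated". Section 8 allows release only with normal vital signs and an alert state.
6. **Upper bound on the cost of alignment.** There is one morphine injection per man at Visit 2, so the added time per role is at most 0.5 h × 80 completers = 40 h, or 0.5 h × 120 at the accrual ceiling = 60 h.

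**The case against.** The strongest case against the point is that item 1 sets a period of required presence and does not tell anyone to leave at 30 minutes. Being in the room and monitoring are separate duties, so a 30-minute in-room minimum can coexist with 60 minutes of physician monitoring. The appendix calls its numbers guidelines. The two appendices are separate site plans that differ elsewhere, for example in naloxone doses and the distress bell, and a man in a scanner is harder to observe and reach. The men have also taken opioids before.

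Much of this stands. It means that no sentence in the protocol is made false and that the matter is minor. It does not explain the figure: Appendix XI carries the same guideline note, and the documents never give the scanner as the reason for its longer time.

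Two stronger readings are tempting and neither is supported:

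- A reader might infer that participants are left unsupervised after 30 minutes. Sections 4d, 7 and 8 rule that out.
- A reader might note that the Visit 2 table schedules DEQ ratings at 40, 50 and 60 minutes and the VAS at 60 minutes, and conclude that Appendix X is in error or that data would be lost. The PET table does the same to Appendix XI: vital signs are recorded at 70, 80, 90 and 95 minutes, and the VAS comes at the end of scanning, all beyond its 60-minute window. Neither window was set to cover its session's full schedule, so items falling after 30 minutes are not evidence of a mistake. The body text requires those measurements regardless.

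**Conclusion.** The point holds as a minor safety-consistency improvement. Appendix X states 30 minutes less in-room attendance than Appendix XI for the same dose. Only the 60-minute figure agrees with the physician monitoring described in the body text, and the shorter figure is unexplained. There is no effect on sample size, power, significance level or any analysis.

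The conclusion rests on two readings. The first is that Appendix X applies to Visit 2, which its title and the Visit 2 location support. The second is that the body text's 60 minutes is the usual minimum, extended when values are abnormal. The Visit 2 table supports this, since it runs to 60 minutes and adds later recordings only if values are out of range. A site-specific reason for 30 minutes may exist; if so, stating it would settle the matter equally well.

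**What to change.** In Appendix X, Plan item 1, replace 30 with 60 as the number of minutes after the injection, and leave the rest of the sentence as it is. No condition about values still outside normal ranges needs adding. Appendix XI, Plan item 1 has none, and Sections 4d and 7 already deal with that case.

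The change is one figure in one line. It needs no staff beyond those already listed. The downside is at most 30 more in-room minutes per Visit 2 morphine injection, within the 40 to 60 hour bound per role. The net addition should be well below that, because nurse and physician monitoring to 60 minutes is already promised and the later ratings already need someone to administer them.

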The study will require at least 4 visits by the participants. Each visit will last approximately 5-8 hours. Visits 1 (consent visit) and 2 (toleration visit) will be at the BRC in Baltimore, the other two visits (Visits 3 and 4) will be conducted in the NIAAA Outpatient clinic and the PET scanning facility of the Clinical Center in Bethesda. The

first two visits will be outpatient visits. Participation in 10-DA-N457 will be encouraged, but not required. Protocol 10-DA-N457 provides for more generalized genetic testing in conjunction with other neuropsychological tasks. Each participant will be scheduled for structural, resting state and diffusion tensor imaging MRI scans on one of the study days or on a separate day if that is not possible in Baltimore. The participants will spend the night before each of the PET studies in the NIAAA inpatient ward (1SE Unit) at the NIH Clinical Center.

During the screening visit performed under the screening protocol (06-DA-N415), MMG will screen healthy participants from a population who have had experience with oral prescription analgesics to obtain samples of two groups of subjects: 1) subjects homozygous for the major 118A allele (118AA genotype) of the OPRM1 polymorphism; 2) subjects carrying one or two copies of the variant 118G allele (118AG or 118GG genotype, hereafter called 118GX) of the OPRM1 polymorphism. At the time of consent to 13-AA-0061 the entire study will be explained and the participant given the opportunity to enroll in the study. During the consent visit (hereafter called Visit 1 of the protocol) or the next visit, participants will be given a questionnaire to evaluate his previous response to oral prescription analgesics (See Appendix I). During Visit 1 or another visit, the participant will undergo the MRI portion of the study.

During Visit 2, participants, who successfully pass the initial screening and enroll in the study after the consent interview, will receive a placebo injection and subsequently a standardized opiate challenge. The opiate challenge will be a standardized IV injection of morphine, (10.0 mg/70 kg; 2 mg/ml) administered over 1 minute.

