Participants may remove their hands when the pain becomes too much to continue. There is a 3 min cut-off, which eliminates any potential damage to the hand. The participant is instructed to immerse his hand in the ice water for up to 3 min, but could withdraw the hand at any time if the pain becomes too great. Participants are instructed

to report verbally when they first sensed pain. This time measures pain threshold. Time to withdrawal measures pain endurance.

IV placement and Blood sampling:

Minor discomfort is expected to result from blood draws and placement of IV lines. These procedures will be performed by qualified and credentialed NIH physicians, nurses, or technicians. Pressure will be applied to IV sites after lines are withdrawn to prevent subcutaneous bleeding. This follows standard clinical routine, and is considered to be a minimal risk/discomfort procedure. Less than 450 ml of blood will be drawn as part of this research study.

Autosense:

Wearing the AutoSense belt may be inconvenient. Participants may also experience slight discomfort and/or minor skin irritation while wearing the belt and electrodes.

8. Subject monitoring

Participants will be monitored by the medical, nursing and research staff for any untoward effect and the study session will be terminated for the participant if any major or unexpected adverse events occur. Oxygen saturation and heart rate will be monitored continuously throughout the study session. Respiratory rate and blood pressure will be monitored every 5 minutes. The MAI or another NIH Credentialed physician with ACLS certification will perform the morphine administration.

Participants will be assessed at the end of the day of Visits 2, 3 and 4 and will not be released until staff can document normal vital signs, an alert and oriented demeanor as well as a normal pupil response to light and have received clearance from attending study investigator (MD). Any impairment in locomotor coordination or judgment will be monitored by the nursing and research staff. The participant will be sent home in a cab paid for by the NIH.

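### Appendix X (outpatient Visit 2) calls 911 only when naloxone fails, and sets no minimum observation time for a man who responds to it

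*Combined protocol and SAP*

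**What the plan says.** Section 4a describes Visits 1 and 2 as taking place at the BRC in Baltimore and says that the "first two visits will be outpatient visits". Visit 2 includes the study's first morphine injection.

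Appendix X, Plan, step 4 covers a man whose oxygen saturation stays below 90%, whose respiration falls below 8 breaths per minute, or who is hard to arouse. Oxygen comes first, then: "If no improvement, administer Naloxone 0.2-0.4mg IV/IM/SC". Doses may be repeated every 2-3 minutes if there is no response. The step gives naloxone's half-life as 30-90 minutes and says "naloxone will be repeated if vital signs or participant condition indicates re-sedation prior to arrival of emergency personnel". Two lines follow: "If participant does not respond to above measures, call 911", with transfer to an emergency room, and disqualification from the study.

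Appendix XI, Plan, step 4b, for the PET visits at the Clinical Center, reads "If no improvement, administer Naloxone 0.4mg IV/IM/SC and call the Code team".

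Monitoring and release at Visit 2 are governed by general rules:

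- Section 4d (Visit 2): physician monitoring after morphine "for the next 60 min or until HR, RR, BP, EKG and oxygen saturation have returned to normal ranges".
- Section 4d (just before the Visit 2 heading): a meal once measurements are complete, then orthostatic vital signs, then discharge if there is no symptomatic orthostasis.
- Section 7: "They will be supervised on site until any signs of drug effect have dissipated", and the man reports no drug effect; he then goes home by taxi.
- Section 8: men are assessed when the visit day ends and "will not be released until staff can document normal vital signs, an alert and oriented demeanor as well as a normal pupil response". Clearance by the study physician is also required.

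**The concern.** The sentence on re-sedation and the 911 trigger in Appendix X do not fit together. The first expects emergency personnel to be on their way. The second summons them only for a man whom naloxone has not helped. If the trigger is followed as written, a man who is successfully reversed stays at an outpatient site with no escalation, and the only further instruction about him is that he leaves the study.

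His release then falls to the general rules. They ask about vital signs, alertness, pupils, impairment and self-reported drug effect, which are the signs that naloxone reverses. He could satisfy them while naloxone is active and become sedated again later without monitoring. Section 7 names respiratory depression as the most important adverse effect of morphine and says it can be fatal if not properly monitored and treated. Few men would be involved, but they are the ones who reacted worst.

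**Working it through.** The plan gives no figure to reproduce here. The check sets the texts side by side, with two small calculations.

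**1. Who is called, and when**

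| | Visit 2 (Appendix X) | PET visits (Appendix XI) |
|---|---|---|
| Setting | Outpatient, BRC | Clinical Center |
| First naloxone dose | 0.2-0.4 mg if oxygen fails | 0.4 mg if oxygen fails |
| Help called | Only on non-response | With the first naloxone dose |
| Repeat naloxone on re-sedation until help arrives | Yes | Yes |

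The re-sedation sentence is common to both plans. In Appendix XI it works, because help is already coming. In Appendix X, for a man who responds, it has no counterpart: nobody has been called.

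**2. Whether any clock runs from naloxone**

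The Visit 2 times run from the morphine injection: credentialed staff in the room until 30 minutes (Appendix X, step 1), and physician monitoring for 60 minutes or until values are normal (Section 4d). Neither restarts when naloxone is given. Sections 7 and 8 and the meal and orthostatic check carry no clock time. So no visible text fixes an interval after the last naloxone dose.

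**3. What the release criteria measure**

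Normal vital signs, alertness, pupil response, absence of impairment and of self-reported effect, and absence of symptomatic orthostasis all describe the man at that moment. Appendix X itself accepts that a restored state can be lost as naloxone wears off. Physician clearance is the one criterion of another kind, and it has no time or naloxone condition attached.

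**4. How many men**

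Section 7 puts respiratory depression after surgery below 1 in 100. Men injected at Visit 2 should number between the 80 completers and the accrual ceiling of 120.

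- 0.01 × 80 = 0.8
- 0.01 × 120 = 1.2

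So fewer than about one man is expected to have respiratory depression of any kind. Those who also fail oxygen, receive naloxone and respond are a subset. This is a rough proxy, since the source population is surgical patients and this sample is screened healthy volunteers.

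**5. What an example hold would achieve**

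Fraction of naloxone remaining = 0.5^(t / half-life), assuming first-order decay and the plan's half-life. At t = 240 minutes after the last dose:

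- half-life 30 min: 0.5^(240/30) = 0.5^8 = 0.004, or 0.4%
- half-life 90 min: 0.5^(240/90) = 0.5^2.67 = 0.157, or 16%

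Four hours is only an example, borrowed from the label's repeat-dosing interval for morphine in Section 7. The calculation shows that little naloxone would remain to mask signs. It does not show that morphine's effect has ended, because the documents do not give its duration.

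**The case against.** The best reply is that the plan already controls release by criteria and a physician's decision, and that Appendix X is an expressly flexible guideline to be used with clinical judgment. Morphine is given in the early afternoon, the meal and orthostatic check come after the measurements, and the assessment comes when the visit day ends. The clearing physician works under a plan that names naloxone's short half-life. Appendix XI sets no post-naloxone clock either. All of this stands and lowers the risk. None of it supplies a naloxone-specific minimum, and Appendix XI at least has the Code team called at once inside a hospital.

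A second reply is that the re-sedation sentence implies help is meant to be called once naloxone is used, or that a man who re-sedates counts as a non-responder. Either reading is possible. If the first was intended, the written trigger does not deliver it. Under the second, help is called only after re-sedation is noticed, which requires that he still be under observation.

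A reader might infer that men can be sent home 60 minutes after morphine, and might take the share of naloxone left at that time as the size of the risk. The documents do not support this. Sixty minutes is a monitoring and recording period, not a release time, and naloxone remaining does not measure re-sedation risk without morphine's remaining effect.

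**Conclusion.** The concern holds as a gap in the written rule. Appendix X's explicit 911 trigger conflicts with its own re-sedation sentence and is weaker than the corresponding step in Appendix XI. A man who responds to naloxone at the outpatient visit has no stated minimum observation time. It is an inexpensive safety improvement that probably concerns one man or fewer and has no bearing on the trial's results.

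The conclusion rests on the visible text. Some pages were removed from the public document, and the morphine package insert is attached but not shown; either could hold a rule. Judging by the contents list, the pages removed just before Appendix X belong to the inpatient nursing sheet. Appendix X itself is present.

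Two stronger readings go beyond the documents. One is that staff would release a reversed man early; nothing shows this, and physician clearance is a real safeguard. The other is to turn the absence of serious adverse events in the 65 subjects cited in Section 7 into an upper limit on the men affected. A serious adverse event is not the same event as naloxone use with response, so such a limit would not describe this group.

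**What to change.** In Appendix X, Plan, step 4:

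1. Call emergency services with the first naloxone dose, matching the Code team call in Appendix XI, step 4b. The re-sedation sentence then works as written.
2. If the man is not transferred, keep him continuously monitored for a stated minimum time after the last naloxone dose, and apply the release criteria of Sections 4d, 7 and 8 only after that. The sponsor should set the time on clinical grounds, taking morphine's duration into account; 4 hours serves only as an example.

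The cost is two or three sentences of text, plus an emergency call or a few hours of extra monitoring for probably one man or fewer. Other participants, the outcomes, the sample size and the analysis are unaffected.
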